The first objective of this period is to standardize the pediatric tubes phlebotomy process. Study procedures will be presented to the ICU nurses by email, printed material, and lectures. Information will include the type of pediatric tube and the blood volume needed for each test, and the importance to collect only the total estimated blood volume according to the tests that need to be performed. Pocket size cards that include the suggested volume of blood to be drawn for each pediatric tube will be provided. No guidance regarding the phlebotomy process when using adult size tubes will be given so that it reflects usual practice. The volume of fluid

drawn to clear the intravenous line will be returned to the patient in a sterile fashion in both groups whenever possible. The frequency and type of blood tests performed will follow usual practice.

The second objective of the pre-intervention period is to provide RBC transfusions recommendations to the ICU physicians. This will be accomplished by email and during any of the regular Critical Care Division meetings. An RBC transfusion will be recommended if the hemoglobin is less than 7 g/dL or if there is bleeding with associated hemodynamic instability regardless of the hemoglobin level. It will be dependent upon the ICU physician to make the final determination regarding the need of any transfusions.

Intervention period (5-11 months)

Blood tests will be collected using pediatric and adult phlebotomy tubes in the experimental and control groups, respectively (Table 1). Arterial blood gases, blood cultures, and lactate levels will be collected using the same tubes in both groups. The exposure period will be from randomization until the hemoglobin is less than 7 g/dL, an RBC transfusion order is placed, the patient is discharged from the ICU (time of an acceptance note) or dies (time of death), clinical bleeding or surgery occur, comfort care measures only are initiated, or the patient stays in the ICU for more than 30 consecutive days.

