3.5 Outcomes

Primary

The primary outcome will be the time from randomization to hemoglobin less than 7 g/dL or RBC transfusion order.

Secondary

The main secondary outcome will be the rate of change in hemoglobin (g/dL/patient/day) in the ICU. This will be calculated as the most recent hemoglobin prior to randomization minus the last hemoglobin prior to ICU discharge, death, RBC transfusion, clinical bleeding, surgery, or change of clinical status to comfort measures, divided by the number of days (rounded to the nearest 0.5) between these two values (crude estimate). If the longitudinal measures of hemoglobin levels deviate substantially from a linear trajectory, we will use a growth model to capture the best fitting function of time (see Analysis Plan for details) and generate a predicted rate of change.

Other secondary outcomes will be the proportion of participants receiving an RBC transfusion while in the ICU, the proportion of patients with at least one inadequate blood sample for laboratory analysis, and the ICU mortality. An inadequate blood sample is defined as any blood sample that requires recollection.

The patient's admission height and weight will be used to estimate the total blood volume of each patient based on Nadler's equation.¹¹ The total daily phlebotomy volume per participant will be calculated based on the number of blood tests per patient per day and the minimal blood volume for analysis of each test.

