3.7 Analysis plan

Baseline variables (e.g. gender, race, age) between groups will be examined for clinically significant differences that may have occurred by chance. If a clinically significant difference is noted, both unadjusted and adjusted analyses will be performed.

Intent-to-treat analyses will be used. The primary outcome will be assessed using time to event analysis with the Cox proportional hazard model including treatment group and ICU admission hemoglobin level group (stratifying variable). Censoring events will be death, ICU discharge, clinical bleeding, surgery, initiation of comfort care measures, and end of the study. We will report the hazard ratio and 95% confidence interval (CI).

We will assess whether the longitudinal measures of hemoglobin follow a linear trajectory. If they substantially deviate, we will employ multilevel mixed models including a quadratic term for time or splines to capture the non-linear change while accounting for within-subject correlation. We will generate predicted rates of change to compare between the study groups.

To compare the rate of change in hemoglobin (either crude or predicted) between the two study groups, a linear regression model will be used with treatment and ICU admission hemoglobin groups as covariates. Multiple regression analysis will be used to assess the relationship between the rate of change in hemoglobin as the dependent variable, and age, admission hemoglobin, acute physiology and chronic health evaluation (APACHE) II score, acute or chronic renal disease, sepsis admission diagnosis, use of medications that can cause bleeding, intervention group, and ICU admission hemoglobin group as independent variables. Proportions of RBC transfusion and proportions of at least one inadequate blood sample will be compared among the two groups using logistic regression models with treatment group and ICU admission hemoglobin level group as covariates.

Sample Size

It is estimated that the primary outcome will occur in about 20-40% of the participants in the control group.^{1,2,6,12-14} A total of 200 patients (100 in each group) will be randomized in the study. This number of participants was chosen to allow completion of the study in a reasonable time frame while obtaining preliminary information to estimate an unbiased treatment effect. This sample size allows a reasonable width of the 95% CI for the rate of the primary outcome in each group (+/- 8%).

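### If hemoglobin trajectories are curved, regressing mixed-model predicted rates as if they were observed gives too small a standard error or an attenuated treatment effect

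*Combined protocol and SAP*

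**What the plan says.** Section 3.5 defines the outcome at patient level: "The main secondary outcome will be the rate of change in hemoglobin (g/dL/patient/day) in the ICU". The default is a crude two-point slope. The alternative is conditional: "If the longitudinal measures of hemoglobin levels deviate substantially from a linear trajectory, we will use a growth model", from which a predicted rate is generated.

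Section 3.7 describes that branch: "If they substantially deviate, we will employ multilevel mixed models including a quadratic term for time or splines". It continues: "We will generate predicted rates of change to compare between the study groups". The group comparison is then one rule for both kinds of rate: "To compare the rate of change in hemoglobin (either crude or predicted) between the two study groups, a linear regression model will be used". Its covariates are the study arm and the admission hemoglobin stratum. A second analysis takes the same outcome: "Multiple regression analysis will be used to assess the relationship between the rate of change in hemoglobin as the dependent variable", on a covariate list that includes "age, admission hemoglobin, acute physiology and chronic health evaluation (APACHE) II score, acute or chronic renal disease, sepsis admission diagnosis".

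For the first-stage model the plan names only time terms. It does not mention treatment, treatment by time, the random effects, or the interval over which a non-constant rate is taken. It describes no bootstrap, weighting or other device to carry first-stage uncertainty into the second regression.

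**The concern.** A regression on treatment, stratum and patient covariates needs one value per patient, so the predicted rates must be patient-level predictions from the mixed model. Each is pulled toward the first-stage mean, more strongly when the patient has few values or a short stay. Ordinary regression treats them as measurements and ignores the pull. The result depends on a choice the plan leaves open:

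- **Treatment by time in the first stage.** Each arm is pulled toward its own mean. The difference between arms survives, but the spread within arms is too small, and so is the standard error.
- **No treatment by time.** Both arms are pulled toward a common mean. The difference and its standard error shrink together, so the null test survives, but the estimate is attenuated and its interval is centred on the wrong value.

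In the multiple regression, covariates left out of the first stage are attenuated under either choice.

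This is the main secondary outcome, and section 2.2 lists the hemoglobin rate in each group as an objective. A pilot's estimates and intervals are what a later trial would be planned on. Leaving the first stage unstated also allows a choice, after the data are seen, between two models that err in different ways.

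**Working it through.** The documents give no standard deviation, effect size or standard error for the hemoglobin rate, so there is no figure to reproduce. From the documents: 100 patients per arm (section 3.7) and follow-up over the ICU stay to at most 30 days (synopsis). Everything else below is assumed.

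**1. Algebra, balanced case.** Let τ be the between-patient slope SD, v the error variance of one patient's fitted slope, n the number per arm and Δ the true difference. The weight given to the patient's own data is λ = τ²/(τ² + v).

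- Variance of predicted slopes within an arm: λ²(τ² + v) = λτ².
- With treatment by time, the second-stage SE is √(2λτ²/n). The actual SD of the difference is √(2(τ² + v)/n) = √(2τ²/(λn)). Their ratio is λ.
- Without it, the expected estimate is λΔ.

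So one quantity governs both harms. With the interaction, two-sided 5% type I error becomes about 2Φ(−1.96λ).

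Illustration: τ = 0.15, residual SD 0.5, five daily values. The sum of squares of time about its mean is 10, so v = 0.25/10 = 0.025 and λ = 0.0225/(0.0225 + 0.025) = 0.47.

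**2. Simulation with a quadratic curve** (100 per arm, daily hemoglobin, unequal stays of 2-30 days, variance components treated as known, 500 runs per scenario, true difference 0 or 0.10 g/dL/day):

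| Slope SD, residual SD, mean stay | SE / actual SD, with interaction | 2Φ(−1.96 × ratio) | Simulated type I error | Estimate of 0.10, without interaction |
|---|---|---|---|---|
| 0.15, 0.5, 5 days | 0.47 | 0.36 | 0.36 | 0.048 |
| 0.15, 0.5, 8 days | 0.63 | 0.22 | 0.23 | 0.065 |
| 0.10, 0.6, 4 days | 0.19 | 0.71 | 0.72 | 0.022 |
| 0.25, 0.3, 8 days | 0.89 | 0.08 | 0.08 | 0.089 |

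The SE ratio and the fraction of the effect retained nearly agree in each row, as the algebra predicts. With the interaction, the mean estimate was 0.100-0.101. Without it, type I error was 0.04-0.05. The contrast taken directly from the mixed model gave 0.100-0.101, coverage 0.952-0.968 and type I error 0.032-0.048.

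**3. Simulation with a bent curve and variances estimated by REML.** There were 24 scenarios: residual SD 0.3 or 0.5; slope SD 0.15, 0.25 or 0.30; median stay 3 or 5 days; hemoglobin every 12 or 24 hours. Each was run 400 times at a true effect of 0 and of 0.10. Mean decline was 0.40/day to day 3, then 0.10/day, and follow-up stopped at the first value below 7.

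| Analysis | Estimate of 0.10 | CI coverage | Type I error |
|---|---|---|---|
| Two-stage, with interaction | 0.095-0.110 | not tabulated; SE is 31-86% of actual SD | 9.5-56% |
| Two-stage, without interaction | 0.038-0.091 | 6-96% | 3.5-7.5% |
| One-stage contrast | 0.096-0.105 | 92-97% | 3.5-7.2% |
| Crude slope | 0.103-0.122 | 93.5-97% | not tabulated |

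Formula check: 2Φ(−1.96 × 0.31) = 0.54 and 2Φ(−1.96 × 0.86) = 0.09, close to the simulated 56% and 9.5%. Without the interaction, power was 34-98%, against 34-96% for one-stage. In the multiple regression, a covariate with true coefficient 0.050 per SD was estimated as 0.017-0.044 under either choice.

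**4. A mild case.** With residual SD 0.2, slope SD 0.40, median stay 5 days and 12-hourly values, type I error was 6-8% with the interaction. Without it, the estimate was 0.099 against 0.106 for one-stage on the same trials: 1 − 0.099/0.106 = 7% attenuation.

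**The case against.** The mechanism is hard to dispute. The objections concern scope, size and remedy.

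- **Multiple regression.** The phrase covering both crude and predicted rates stands only in the group-comparison sentence. That is so, but section 3.5 replaces the outcome itself in the curved branch, so the multiple regression inherits it. Attenuation of age or APACHE II does assume that they are absent from the first stage, where only time terms are named.
- **Size.** Nothing in the documents places the trial in the mild or the severe region. This stands: the ranges are not bounds. The mild case's 7% is also measured against the one-stage estimate; against the true 0.10, the two-stage figure of 0.099 is only 1% low.
- **Window.** The bent-curve simulations stop at hemoglobin below 7, following the exposure rule ("The exposure period will be from randomization until the hemoglobin is less than 7 g/dL"). Section 3.5 does not list that value as an end of the outcome window. Removing the stop changed nothing material.
- **Remedy.** The crude slope behaved well on curved data, so keeping it in both branches would be the smaller edit, and a fixed-interval contrast changes the estimand. This has weight, and is why the crude slope should be reported alongside. But the plan wants a model-based rate when trajectories bend, and a curved trajectory has no single rate until an interval is named.
- **Importance.** This is a fallback for a secondary outcome in a pilot, with no stated alpha or power. That limits the severity but does not make the second-stage regression valid.

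**Conclusion.** The concern holds, conditional on the curved branch being used. Followed as written, the plan then either understates the standard error of the main secondary comparison or attenuates its effect, depending on a first-stage choice it does not state. The direction is firm. The size turns on how precisely each patient's slope is measured: serious with short stays and noisy values, minor when slopes are precise. The figures rest on assumed variances, stays and sampling frequencies. It should be fixed before analysis, but it does not threaten the trial's primary result.

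**What to change.** In the curved branch, drop the second-stage regression of predicted rates and specify in section 3.7:

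1. One linear mixed model on all hemoglobin values in the section 3.5 outcome window, with random intercept and slope, admission hemoglobin stratum and stratum by time, non-linear time terms (splines rather than a single quadratic), and treatment by each time term.
2. The treatment contrast over one fixed interval named before the data are seen, with its model-based confidence interval. Randomization to day 3 is an example only; the documents give no stay data to set it.
3. Covariate by time terms in that same model, in place of the multiple regression on predicted rates.
4. A written criterion for linear versus curved, judged on both arms pooled and blind to allocation.
5. The crude slope as the analysis when trajectories are linear, and reported beside the contrast when they are not.

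Optionally, use unrounded time for the crude slope, because an interval under 0.25 day rounds to a zero denominator, and report a linear mixed-model slope as supportive.

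The cost is SAP wording. No new data are needed, since the plan already fits a mixed model in this branch. Two limits should be stated:

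- **Weighting.** Mixed models give longer stays more weight. In a deliberately strong case (effect 0.15 in stays up to the median and 0.05 in longer ones, equal-weight mean 0.10), a linear mixed model gave 0.067-0.092 and the crude slope 0.093-0.098.
- **Curve shape.** The one-stage contrast depends on the curve fitted. On bent data a quadratic gave 0.072-0.112 for a true 0.10, with 83-95% coverage. Splines with a misplaced knot did better: 0.095-0.108 (coverage 92-98%) for a constant effect, and 0.079-0.097 (coverage 90-96.5%) when the effect fell to 0.025 after day 3. The last range can still be up to 21% low.

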3.2 Participants

Inclusion (all of the following)

- Age \geq 18 years old
- New admission to the medical or transplant ICU at Memorial Hermann Hospital in Houston
- ICU admission hemoglobin level of at least 7 g/dL. The ICU admission hemoglobin will be the most recent hemoglobin value available at the time of screening for inclusion in the study.
- Randomization is expected within 12 hour of admission to the ICU

Exclusion (any of the following)

Conditions that affect the generation or loss of RBCs

- Clinical bleeding. Defined as menstrual bleeding, bleeding leading to a change in the frequency of hemoglobin monitoring or to an order for a medication, transfusion, procedure, or consultation intended to prevent or treat bleeding.
- Known hemolytic disorder (e.g. sickle cell disease, hereditary spherocytosis, autoimmune hemolytic anemia)
- Bone marrow disorder (e.g. aplastic anemia, marrow infiltration disorder, chemotherapy within the last 8 weeks)

Randomization to adult size phlebotomy tubes is not recommended

- Jehovah's Witnesses

Collection of blood tests is not possible or desired

- Patient is comfort care measures only

Inability to complete the desired time of follow up

- Refractory shock: mean arterial blood pressure below 60 mmHg despite maximal doses of 3 vasopressors. Maximal dose of vasopressors are as follows: Norepinephrine 70 mcg/min; vasopressin 0.04 units/min; epinephrine 35 mcg/min; dopamine 20 mcg/kg/min; phenylephrine 350 mcg/min
- Severe acidosis: pH below 7 in more than one arterial blood gas within 24 hours of ICU admission in the absence of diabetic ketoacidosis

Other

- Surgical admission diagnosis
- Pregnancy
- Current prisoner

33 Allocation

All patients admitted to the medical or transplant ICU will be screened for eligibility. Group assignment will be done using the randomization module in the Research electronic data capture (RedCap). Randomization will be stratified by ICU admission hemoglobin level (7 to 9.49 g/dL, 9.5 to 11.99 g/dL, and 12 g/dL or greater). Patients will be randomized using permuted blocks of 4 or 6 and a 1 to 1 ratio, into one of two groups: the pediatric size phlebotomy tubes group or the adult size phlebotomy tubes group.

34 Interventions

Pre-intervention period (1 month)

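### In the supplementary regression, the admission-hemoglobin coefficient is biased in a direction that cannot be known in advance, because the same measurement is normally part of the outcome and follow-up stops at low hemoglobin

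*Combined protocol and SAP*

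**What the plan says.** Section 3.5 defines the crude rate of change as "the most recent hemoglobin prior to randomization minus the last hemoglobin prior to ICU discharge, death, RBC transfusion, clinical bleeding, surgery" or a move to comfort care, divided by the days between the two values, rounded to half a day. A positive value is a loss.

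Section 3.2 defines the admission value: "The ICU admission hemoglobin will be the most recent hemoglobin value available at the time of screening for inclusion in the study". Because patients should be randomized no later than 12 hours after reaching the ICU, this is normally the same measurement as the last one before randomization. The exception is a patient with a new result between screening and randomization.

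Section 3.7 has two regressions on this rate. The first, introduced by "To compare the rate of change in hemoglobin (either crude or predicted) between the two study groups", adjusts for treatment and hemoglobin group only. The second is supplementary and assesses predictors. It uses "the rate of change in hemoglobin as the dependent variable, and age, admission hemoglobin" and further clinical factors, ending with "intervention group, and ICU admission hemoglobin group as independent variables". Hemoglobin therefore enters it both as a continuous value and as a band.

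Section 3.4 ends exposure at hemoglobin below 7 g/dL or a transfusion order, among other events. Nothing in the plan cautions against interpreting the admission-hemoglobin coefficient.

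**The concern.** Two mechanisms distort this coefficient even if true loss has nothing to do with starting hemoglobin.

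- **Coupling.** A baseline value that is high by chance inflates both the predictor and the apparent fall. This mathematical coupling, with regression to the mean, gives a positive bias.
- **Stopping on the outcome.** Patients who start near 7 g/dL are more likely to be cut off, and are cut off on a low reading. Their apparent loss per day is exaggerated, which gives a negative bias.

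The purpose of this model is to describe how each predictor relates to loss. The pilot could therefore report a gradient by admission hemoglobin, in either direction, that is wholly artefact, and carry it into planning of the larger trial.

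**Working it through.** The documents give no figure for this regression and none for measurement error, so there is nothing to reproduce.

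**Assumptions (not in the documents).** True baseline SD 2 g/dL; true loss 0.2 g/dL/day (SD 0.15), unrelated to baseline; daily hemoglobin; length of stay log-normal with log-scale SD 0.6; no treatment effect. From the documents: n = 200 and entry at 7 g/dL or above.

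**Step 1: coupling alone, closed form.** Without stopping, the false coefficient is

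σe² / (σb² + σe²) × mean(1/days).

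For a median stay of 4 days, mean(1/days) ≈ exp(0.18)/4 = 0.299. At within-patient SD 0.5: 0.25/4.25 × 0.299 = 0.0588 × 0.299 = 0.018 g/dL/day per g/dL. At SD 0.3: 0.09/4.09 × 0.299 = 0.007. At SD 0.7: 0.49/4.49 × 0.299 = 0.033.

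**Step 2: the same setting by simulation (mean hemoglobin 10.5, median stay 4 days).** "Sig. +" is the share of trials with a significant positive coefficient in a two-sided 5% test (2.5% expected).

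| Within-patient SD | No stop, no group term | Sig. + | No stop, with group term | Sig. + | Stop at <7, with group term |
|---|---|---|---|---|---|
| 0.3 | +0.007 | 13% | +0.006 | 5% | -0.006 |
| 0.5 | +0.018 | 34% | +0.018 | 8% | -0.004 |
| 0.7 | +0.033 | 62% | +0.034 | 15% | +0.004 |

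With zero measurement noise the coefficient is 0.000, so the shared term does no harm without error in it. Replacing the covariate by a separate baseline measurement (no stop, no group term) removes the positive bias: -0.0015, -0.0038 and -0.0067 at the three SDs.

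**Step 3: stopping at the first value below 7, by event share.** Ranges are over within-patient SD 0.3 to 0.7.

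| Simulated events | Setting | No group term | With group term |
|---|---|---|---|
| 3-5% | mean 11.5, median 3 days | +0.006 to +0.030 | +0.006 to +0.035 |
| 7-10% | mean 10.5, median 3 days | +0.003 to +0.018 | -0.002 to +0.017 |
| 25-32% | mean 9.5, median 6 days | -0.012 to -0.035 | -0.024 to -0.037 |

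One further setting reached the plan's range: mean 10.5, median 6 days, SD 0.7, 21% events. It gave -0.015 without the group term and -0.009 with it. In the 25-32% row, the coefficient was falsely significant and negative in 28-49% of trials without the group term and 11-22% with it.

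**Step 4: size in practice.** At SD 0.5 without the group term, the coefficient runs from -0.0244 (28% events) to +0.0162 (4% events). Between patients 4 g/dL apart, that is 4 × -0.0244 = -0.098 to 4 × 0.0162 = +0.065 g/dL/day, against an assumed true loss of 0.2.

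**Step 5: the treatment term.** In the base setting it stayed near zero, with type I error of about 4-6%.

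**The case against.** A reader might infer that this regression will show higher-hemoglobin patients losing hemoglobin faster. The documents do not support that. Section 3.7 expects the primary outcome in 20-40% of controls, and in the simulated settings within that range the bias was negative. The positive sign persisted where events were rarer. Section 3.7 also enters the hemoglobin group, which is collinear with the continuous value and makes an individually significant coefficient less likely. Both points stand.

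They do not rescue the coefficient. Without stopping, the group term leaves the mean bias almost unchanged and mainly widens its standard error. A joint test of all hemoglobin terms still rejected in 10%, 21% and 45% of trials at SD 0.3, 0.5 and 0.7. Where the two biases cancel, they do so by accident.

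The plan also allows a model-predicted rate in place of the crude one, but only if trajectories depart substantially from linear. A least-squares slope through all values including baseline still gave +0.006 to +0.029 without stopping.

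Two further inferences should be resisted. The randomized comparison is not biased by this: the main model contains only treatment and hemoglobin group. Nor does this regression answer the section 2.2 objective on which admission range predicts benefit. That is a treatment-by-hemoglobin question, and the model has no interaction term.

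**Conclusion.** The point holds in a limited form. The admission-hemoglobin coefficient mixes a positive bias from error in the shared baseline value with a negative bias from stopping at low hemoglobin. When there is no true relation, it may show higher-hemoglobin patients losing faster, losing slower, or neither. The size and sign depend on baseline measurement error, which the documents do not give, and on the event rate. Across the simulated settings with stopping and SD 0.3 to 0.7, it ranged from about -0.037 to +0.035 g/dL/day per g/dL.

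These figures rest on the assumed SDs, loss rate and lengths of stay. They also assume that the rate stops at the first value below 7 g/dL. That is uncertain, because the end events listed for the rate in section 3.5 omit this criterion while section 3.4 includes it; the two lists need to be reconciled.

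Severity is consider: the model is supplementary and the treatment effect is untouched.

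**What to change.** In section 3.7, estimate the relation between starting hemoglobin and rate of loss as the intercept-slope covariance of a random-intercept, random-slope mixed model. Fit it to all observed hemoglobin values, including the value that ends follow-up, so that stopping depends on data the model contains. In a check simulation the intercept-slope relation was near zero both with stopping (-0.0025) and without (+0.0025), within about 1.6 simulation standard errors. State also that the admission-hemoglobin coefficient from the baseline-minus-last rate will not be interpreted.

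A rate computed from post-randomization values only should not be the sole remedy. It removes the coupling but leaves the stopping bias unopposed. In one set of runs with 20-25% events (mean hemoglobin 10, SD 0.5, no group term), the coefficient moved from -0.008 to -0.029, and false significant negative results rose from 11% to 42%.

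The cost is a few lines of plan text, slightly more analysis work, and a covariance that will be estimated imprecisely with 200 patients.

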1. BACKGROUND AND RATIONALE

Anemia and red blood cells (RBC) transfusions are common in critically ill patients.^{1,2} One factor associated with the development of anemia^{3,4} and RBC transfusions^{5,6} in these patients is the volume of diagnostic phlebotomy. Therefore, a more efficient use of blood drawn for diagnostic testing has the potential to reduce transfusions.

Even though blood conserving strategies could be beneficial, there are no randomized controlled trials (RCTs) assessing their efficacy in reducing RBC transfusions in adults. A blood conserving arterial line system reduced the RBC transfusion volume in an RCT of very low birth weight infants.⁷ However, the results of this trial might not be applicable to adults as their larger circulating blood volume might limit the benefit of any blood conserving intervention.⁸

The use of pediatric size phlebotomy tubes has been proposed to reduce anemia and RBC transfusions in adults. Adult phlebotomy volumes exceed pediatric ones for the same tests.⁹ However, the absence of high quality data supporting their efficacy compounded by the loss of automation in the processing of pediatric tubes prevents their routine use. Two RCTs assessed their effect on the change in hemoglobin in adults. The first trial showed no benefit, but the intervention was limited to basic metabolic profile tubes and the study was conducted in a general Internal Medicine population.⁸ The second trial, performed in the Intensive Care Unit (ICU) setting, demonstrated a reduction in the decline of

hemoglobin, but used a co-intervention.¹⁰ None of these studies analyzed the change in hemoglobin as a function of time at risk.

An RCT is needed to evaluate the hypothesis that the use of pediatric size phlebotomy tubes reduces RBC transfusions in adult ICU patients compared with the use of adult size tubes. However, its design is complicated by the lack of knowledge regarding the expected effect size and overall feasibility of this intervention. Thus, we will perform a pilot RCT that will allow us to investigate these issues.

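### The ±8% confidence interval half-width has no stated event rate and holds only at the low end of the plan's own 20–40% control range

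*Combined protocol and SAP*

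**What the plan says.** The relevant statements are all in the Sample Size paragraph of section 3.7 (Analysis plan).

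- **Size:** "A total of 200 patients (100 in each group) will be randomized in the study".
- **Expected rate:** "the primary outcome will occur in about 20-40% of the participants in the control group". No rate is given for the pediatric-tube group.
- **Reason for the size:** "This number of participants was chosen to allow completion of the study in a reasonable time frame", along with preliminary information for estimating the treatment effect.
- **Precision:** "This sample size allows a reasonable width of the 95% CI for the rate of the primary outcome in each group (+/- 8" percent).

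The plan gives no power calculation, no target effect and no other precision figure. Nothing elsewhere in the document says which event rate or interval method lies behind the 8%.

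**The concern.** The width of a confidence interval for a proportion depends on the proportion. Between 20% and 40% it grows as the rate rises. A single unconditional half-width placed after a 20–40% range therefore reads as holding across that range, and it cannot do so with a fixed 100 patients per group.

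This matters because the trial is a pilot whose purpose is estimation, and this sentence is the only quantitative support for enrolling 200 patients. If the figure matches only the most favourable end of the assumed range, readers will expect a more precise control-group rate than the design is likely to give. Only the planning statement is affected.

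**Working it through.** **Inputs.** n = 100 per group, 95% confidence, a control rate p of 20–40% and a stated half-width of 8 points, all from the Sample Size paragraph of section 3.7. The Allocation subsection confirms 1:1 randomization.

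**Step 1: reproduce the stated figure.** The Wald half-width is 1.96 × √(p(1−p)/n). At p = 0.20:

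1.96 × √(0.20 × 0.80 / 100) = 1.96 × 0.0400 = 0.0784, or 7.8 points.

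This rounds to 8, so the plan's figure is reproduced at 20%.

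**Step 2: the rest of the stated range** (half-widths in percentage points, n = 100).

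| Event rate | Wald | Wilson | Exact (Clopper-Pearson) | n per group for ±8 (Wald) |
|---|---|---|---|---|
| 20% | 7.8 | 7.8 | 8.3 | 97 |
| 25% | 8.5 | 8.4 | 8.9 | 113 |
| 30% | 9.0 | 8.8 | 9.4 | 127 |
| 40% | 9.6 | 9.4 | 10.0 | 145 |

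The exact interval is asymmetric, so its entry is half the total width. The last column is 1.96² × p(1−p) / 0.08², rounded up.

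**Step 3: where ±8 stops holding.** The Wald half-width equals 8.0 at p = 21.1% and reaches the rounding limit of 8.5 at p = 25.1%. The share of the control range above 25% is (40 − 25)/(40 − 20) = 0.75. The cut-off depends on the method: the exact half-width is already 8.53 at 22%. By 30%, none of the three methods gives a figure that rounds to 8.

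**Step 4: what ±8 points amounts to at higher rates.** The standard error is 4.58 points at 30% and 4.90 at 40%.

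- At 30%: z = 8/4.58 = 1.75, about a 92% interval.
- At 40%: z = 8/4.90 = 1.63, about a 90% interval. The Wald 95% interval there is 30.4–49.6%, compared with the 32–48% implied by ±8.

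**Step 5: could pooling explain the figure?** With n = 200, the Wald half-width is 5.5 points at 20% and 6.8 at 40%. It does not.

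**Step 6: the pediatric-tube group.** The plan gives no rate, so the hazard ratios (HR) here are assumptions for illustration. Under proportional hazards and common follow-up, the treated rate is 1 − (1 − p_control)^HR.

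- HR 0.5: rates of 10.6–22.5%, half-widths of 6.0–8.2 points. ±8 is met after rounding across the range.
- HR 0.7: rates of 14.5–30.1%, half-widths of 6.9–9.0 points. ±8 is met while the control rate is below about 34%.

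**The case against.** The strongest reply is that nothing was miscalculated. At 20%, a rate inside the plan's own range, all three methods round to 8, so the gap is an unstated assumption. That describes the origin of the figure correctly. But the sentence carries no condition and claims the precision for each group, including the controls, the only group with a stated rate. As written, it is untrue for most of that range.

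A second reply is that little depends on the figure. The sample size was set by feasibility, the documents set no precision threshold that 9 or 10 points would fail, and no decision rule uses the number. This stands, and it limits the weight of the point.

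Third, the hypothesis in section 1 is that "the use of pediatric size phlebotomy tubes reduces RBC transfusions in adult ICU patients". If so, the pediatric-tube group may well have a rate low enough for ±8 to hold. This also stands, as Step 6 shows, but it does not help the control group.

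Two technical cautions are fair. The 25% cut-off is a Wald result and would be lower with an exact interval. And the binomial formula treats the outcome as a crude proportion, whereas section 3.5 defines a time to event and section 3.7 censors at discharge, death and other events. An interval from a Kaplan-Meier type estimate could be wider. The documents give no figures from which to say by how much.

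**Conclusion.** The concern holds. The ±8% is correct at about 20%, acceptable after rounding up to about 25% (Wald), and too narrow for the control group from there to 40%. The excess is about 1 point at 30% and 1.6 points at 40% (9.6 against 8.0, or 20% in relative terms). The statement may be true for the pediatric-tube group, depending on a rate the plan does not give.

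The conclusion rests on 100 analysed patients per group and a simple binomial proportion. It does not depend on the choice among the three interval methods. This is a small error in the planning text that should be corrected. It does not undermine the design.

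**What to change.** In the Sample Size paragraph of section 3.7, replace the single figure with a conditional statement, for example:

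> With 100 patients per group, the half-width of the 95% CI for the crude proportion with the primary outcome (Wald) is about ±8, ±9 and ±10 percentage points if the event rate is 20%, 30% and 40%.

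Keep the sample size at 200. The cost is one sentence and a slightly less favourable stated precision, with no extra patients and no change to the analysis.

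Optionally, because the primary objective in section 2.1 is an effect size and section 3.7 reports a hazard ratio, add the precision expected for that ratio. Assuming equal event rates in both groups and proportional hazards, the 95% limits are the estimate multiplied and divided by:

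- exp(1.96 × √(1/20 + 1/20)) = 1.86 with 40 events in total (20% in each group);
- exp(1.96 × √(1/40 + 1/40)) = 1.55 with 80 events in total (40% in each group).

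This addition is a suggestion and is not needed to correct the error.
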